APPENDIX H. LEEDS DACTYLITIS INDEX

The LDI basic measures the ratio of the circumference of the affected digit to the circumference of the digit on the opposite hand or foot, using a minimum difference of 10% to define a dactylitic digit.^{7,8} The ratio of circumference is multiplied by a tenderness score, using a modification of LDI which is a binary score (1 for tender, 0 for non-tender). If both sides are considered involved, or the circumference of the contralateral digit cannot be obtained, AbbVie will input and utilize a circumference provided in the standard reference tables. This modification is referred to as LDI basic and will be applied in this study. The LDI requires a finger circumference gauge or a tape measure to measure digital circumference.

Dactylitis Count

The dactylitis count is the number of fingers and toes with dactylitis, with a range of 0 – 20.

Presence of Dactylitis

If dactylitis is present with any finger or toe, the subject is counted as a subject with dactylitis.

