An assessment of 66 joints will be done by directed physical examination. The hip joints are not assessed for swelling; all other joints that are assessed for tenderness will also be assessed for swelling. Joint swelling will be classified as present, absent, replaced, or no assessment. Joints injected with corticosteroid will be considered non-evaluable for 90 days from the time of the injection.

The assessor should be an independent qualified medical professional.

Dactylitis

LDI

This evaluation will be conducted to assess the presence or absence of dactylitis in all 20 of the subject's digits. The assessment should begin with visual inspection of the hands and feet. For each pair of digits in which one or both digits appear dactylitic, the circumference of the affected digits (both right and left side) will be assessed using a dactylometer. Additionally, the affected digit pairs will be assessed for tenderness by squeezing the digital shaft mid-way between the metacarpophalangeal and proximal interphalangeal joints and will be recorded as tenderness, yes or no. Tenderness should not be assessed by squeezing the joint lines. Digits injected with corticosteroid will be considered non-evaluable for 90 days from the time of the injection. If a digit is missing and its contralateral digit is dactylitic, "digit

absent" will be recorded for the missing digit. For any digit without an available dactylometer measurement, the standard reference value will be utilized in calculation of the LDI. The standard reference values will not be entered into the eCRF. A dactylometer will be provided to sites for use.

The assessor should be an independent qualified medical professional.

Enthesitis

LEI

LEI is a validated enthesitis index that uses 6 sites for evaluation of enthesitis: lateral epicondyle humerus left and right, Achilles tendon insertion left and right, and medial condyle femur left and right. Tenderness on examination is recorded as either present, absent, or not assessed for each of the 6 sites, for an overall score range of 0 – 6.

Enthesitis sites injected with corticosteroid will be considered non-evaluable for 90 days from the time of the injection.

The assessor should be an independent qualified medical professional.

SPARCC Enthesitis Index

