3.2 Secondary Endpoints

The following is a list of ranked secondary endpoints with multiplicity adjustment:

1. Change from Baseline in Health Assessment Questionnaire-Disability Index (HAQ-DI) score at Week 24;

2. Psoriasis Area Severity Index (PASI) 90 response at Week 24 (for subjects with BSA \geq 3% at Baseline);
3. ACR20 response at Week 16;
4. Minimal Disease Activity (MDA) response at Week 24;
5. Change from baseline in 36-Item Short Form Health Survey (SF-36) Physical Component Summary (PCS) score at Week 24;
6. Change from baseline in Functional Assessment of Chronic Illness Therapy-Fatigue (FACIT-Fatigue) score at Week 24.

Other secondary endpoints are:

1. ACR50 response at Week 24;
2. ACR70 response at Week 24;
3. Resolution of enthesitis defined as Leeds Enthesitis Index (LEI = 0) at Week 24 (for subjects with baseline presence of enthesitis (LEI > 0));
4. Resolution of dactylitis defined as Leeds Dactylitis Index (LDI = 0) at Week 24 (for subjects with baseline presence of dactylitis (LDI > 0)).

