3.3 Additional Efficacy Endpoints

The primary and secondary efficacy endpoints are listed in Section 3.1 and Section 3.2, respectively. Additional efficacy endpoints at all scheduled visits (when measurements are collected) are listed below.

- ACR20/50/70 response;
- Change from Baseline in individual components of ACR response:
 - Change from Baseline in Tender Joint Count (TJC) (0 - 68);
 - Change from Baseline in Swollen Joint Count (SJC) (0 - 66);

- Change from Baseline in Physician Global Assessment of Disease Activity (PGA) (mm on a 100-mm horizontal visual analogue scale [VAS]);
- Change from Baseline in Patient's Global Assessment of Disease Activity (PtGA) (mm on a 100-mm horizontal visual analogue scale [VAS]);
- Change from Baseline in Patient's Assessment of Pain (mm on a 100-mm horizontal visual analogue scale [VAS]);
- Change from Baseline in Health Assessment Questionnaire - Disability Index (HAQ-DI) score;
- Change from Baseline in High-Sensitivity C Reactive Protein (hs-CRP);
- MDA response;
- Change from Baseline in LDI (for subjects with Baseline LDI > 0);
- Change from Baseline in dactylitis count (for subjects with Baseline LDI > 0);
- Resolution of dactylitis (LDI = 0) (for subjects with Baseline LDI > 0);
- Change from Baseline in LEI (for subjects with Baseline LEI > 0);
- Resolution of enthesitis (LEI = 0) (for subjects with Baseline LEI > 0);
- Change from Baseline in Spondyloarthritis Research Consortium of Canada (SPARCC) Enthesitis Index (for subjects with baseline SPARCC Enthesitis Index > 0);
- Resolution of enthesitis sites included in the SPARCC Enthesitis Index (for subjects with Baseline SPARCC Enthesitis Index > 0);
- Change from Baseline in total enthesitis count (for subjects with baseline LEI > 0 and Baseline SPARCC Enthesitis Index > 0);
- Resolution of enthesitis in both LEI and SPARCC (defined as LEI = 0 and SPARCC = 0) (for subjects with Baseline LEI > 0 and Baseline SPARCC Enthesitis Index > 0);
- PASI 75/90/100 response (for subjects with BSA \geq 3% at Baseline);
- Achievement of both PASI 90 and ACR50 (for subjects with BSA \geq 3% at Baseline);
- Change from Baseline in BSA-PsO (for subjects with BSA \geq 3% at Baseline);
- Modified Psoriatic Arthritis Response Criteria (PsARC);

- Change from Baseline in Disease Activity Score 28 using high sensitivity C Reactive Protein (DAS28-hsCRP);
- Change from Baseline in PsA Disease Activity Score (PASDAS);

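### The only written LDI scoring rule leaves the normal ratio of 1 in every digit's score, so change from Baseline in LDI would mainly follow the number of tender dactylitic digits

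*Protocol*

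**What the plan says.** Operations Manual Appendix H describes the instrument in prose. It starts from a ratio, the affected digit's circumference divided by that of its counterpart on the other side, and sets a cut-off for counting a digit, "using a minimum difference of 10% to define a dactylitic digit". It then gives the scoring step, "The ratio of circumference is multiplied by a tenderness score", with tenderness coded 1 or 0. It closes with "This modification is referred to as LDI basic and will be applied in this study".

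No other passage adds to the rule. Operations Manual Section 3.5 covers measurement and substitution only: "For any digit without an available dactylometer measurement, the standard reference value will be utilized in calculation of the LDI". The SAP uses LDI in three ways and defines the score in none of them:

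- a Week 24 other secondary endpoint, "Resolution of dactylitis defined as Leeds Dactylitis Index (LDI = 0) at Week 24" (Section 3.2);
- change from Baseline in LDI among subjects with Baseline LDI above 0, an additional endpoint listed separately from change in dactylitis count (Section 3.3);
- the Baseline summary of LDI (Section 7.1).

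Neither document mentions subtracting 1, scaling, summing over digits, or whether the 10% criterion is applied again after Baseline.

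**The concern.** A digit the same size as its opposite has a ratio of 1, and a digit counts as dactylitic only from a ratio of 1.10. A programmer who follows Appendix H therefore gives every tender dactylitic digit a fixed 1.00 for normal size plus a small increment for swelling. The increment is the part the dactylometer is there to measure.

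At stake is what the change-from-Baseline LDI endpoint means. Scored this way it sits close to a count of tender dactylitic digits. The study already needs such a count for PASDAS (Operations Manual Appendix M), so the circumference data would add little to it.

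**Working it through.** The plan gives no power or sample-size figure that depends on LDI, so there is no plan figure to reproduce. The check applies the written rule and compares it with scoring the excess.

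**Inputs from the documents.** Digit ratio r = affected / opposite circumference; dactylitic if r is at least 1.10; tenderness t = 0 or 1; digit score as written = r x t (all Operations Manual Appendix H). Comparison score = (r - 1) x t.

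**Step 1: share of the score that is the constant.** For a tender digit with swelling s, r = 1 + s and the share is 1/(1 + s).

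| Swelling | Score as written | Share due to the constant |
|---|---|---|
| 10% | 1.10 | 1/1.10 = 91% |
| 20% | 1.20 | 1/1.20 = 83% |
| 30% | 1.30 | 1/1.30 = 77% |
| 50% | 1.50 | 1/1.50 = 67% |

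**Step 2: response to graded improvement in a digit that stays tender and dactylitic.**

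| Ratio before and after | Fall as written | Fall in excess |
|---|---|---|
| 1.20 to 1.10 | 0.10/1.20 = 8.3% | 50% |
| 1.30 to 1.15 | 0.15/1.30 = 11.5% | 50% |
| 1.40 to 1.20 | 0.20/1.40 = 14.3% | 50% |
| 1.40 to 1.12 | 0.28/1.40 = 20% | 0.28/0.40 = 70% |

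Loss of tenderness removes 100% of the digit's score under either rule.

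**Step 3: how much of the total score is digit count.** The inputs here are assumptions: swelling uniform on 10% to 50%, N = 1 + Poisson(2) tender dactylitic digits, scores summed. Then E(N) = 3, Var(N) = 2 and the digit variance is 0.40²/12 = 0.01333. For a sum of N independent digit scores with mean m and variance v, the share of variance explained by N is Var(N)m² / [Var(N)m² + E(N)v].

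- As written, m = 1.30: 2 x 1.69 = 3.38; 3 x 0.01333 = 0.04; 3.38/3.42 = 0.988.
- Excess, m = 0.30: 2 x 0.09 = 0.18; 0.18/(0.18 + 0.04) = 0.818.

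Varying the upper swelling limit from 30% to 100% and the Poisson mean from 0.5 to 4 gives about 0.92 to 1.00 as written and 0.60 to 0.91 for the excess. These are cross-sectional figures.

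**Step 4: change scores.** A separate simulation looked at change directly. Its assumptions were 20,000 subjects, 4 tender dactylitic digits each, Baseline ratios uniform on 1.10 to 1.50, excess shrinking by a uniform 0 to 100%, tenderness resolving in half the digits, and scores summed. The correlations were:

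| Score and threshold rule | With change in tender dactylitic count | With change in total swelling |
|---|---|---|
| As written, 10% reapplied | 0.98 | 0.33 |
| Excess, 10% reapplied | 0.57 | 0.66 |
| As written, 10% not reapplied | 0.98 | 0.15 |
| Excess, 10% not reapplied | 0.56 | 0.63 |

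**Step 5: the threshold and LDI = 0.** If the 10% criterion is reapplied, a tender digit going from 1.12 to 1.09 drops to 0 under both rules, and LDI = 0 identifies the same subjects. The drop at the threshold is 1.10 as written and 0.10 on the excess scale; on both scales the span from 10% to 50% swelling is 0.40. If the criterion is not reapplied, a tender digit with r = 1.00 scores 1.00 as written and 0 on the excess, so resolution status could differ.

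**The case against.** The strongest reply is that Appendix H is shorthand. It cites two instrument papers, omits summation as well as subtraction, and sits near an appendix (F, DAS28) that lists inputs without a formula. Reading the missing subtraction as the rule while supplying the missing summation is selectively literal. Part of this stands: the cited sources cannot be consulted here, and summation is an assumption in the working. But Appendix H states an actual multiplication and says that it applies in this study. The neighbouring appendices for PASI, PASDAS, DAPSA and ASDAS also print full formulas.

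Four stronger readings are tempting, and the documents do not support them.

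- A reader might infer that the score cannot show a fall in swelling while a digit stays dactylitic. It can: 1.40 to 1.12 is a 20% fall. The response is weak, not absent.
- A reader might infer that LDI merely duplicates the dactylitis count endpoint. That count, as Appendix H defines it, does not require tenderness, so LDI carries something the count lacks.
- A reader might infer that the jump at 10% comes from leaving in the 1. The threshold causes it, if it is reapplied, under either rule; the constant only makes the step larger relative to the graded range.
- A reader might infer that the analysis has been or will be programmed wrongly. The documents show only what the written rule would yield.

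It is also fair to say that digit count still explains most of the cross-sectional variance after the correction, and that the percentages in Steps 3 and 4 depend on assumed inputs. The direction is the same across all the inputs tried.

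**Conclusion.** The point holds as a minor one. Taken literally, the only LDI rule in the documents puts a constant of 1 into each tender dactylitic digit's score, which is 67% to 91% of that score for swelling of 50% down to 10%. Change from Baseline in LDI would then mainly follow the number of tender dactylitic digits and register graded swelling change above 10% only weakly. The shares in Steps 1 and 2 are exact arithmetic on the written rule. The variance shares and correlations are illustrations under stated assumptions.

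The reach is small. Only Baseline LDI and an additional endpoint with nominal p-values (SAP Section 8.5) are affected. The primary and ranked endpoints do not use LDI. The Week 24 LDI = 0 endpoint is unchanged provided the 10% criterion is reapplied after Baseline, which the documents leave open.

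**What to change.** In Operations Manual Appendix H and in the SAP, write out the whole derivation:

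- score each dactylitic digit as (ratio - 1) x tenderness, summed over digits; a factor of 100 would be scaling only and changes no comparison;
- check that expression against the cited instrument source before adopting it, so that the correction does not itself depart from the instrument;
- state whether the 10% criterion is reapplied at each post-Baseline visit. If it is not, the score also needs a rule for ratios below 1, and LDI = 0 needs its own definition.

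The cost is one formula and one sentence. The circumferences and tenderness are already collected, and no visit, sample size or test in the ranked sequence changes. It is best settled before the Week-24 Database Lock.

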APPENDIX I. LEEDS ENTHESITIS INDEX (LEI)

LEI is a validated enthesitis index that uses 6 sites for evaluation of enthesitis: lateral epicondyle humerus left and right, Achilles tendon insertion left and right and medial condyle femur left and right. The LEI demonstrated substantial to excellent agreement with other scores in the indication of psoriatic arthritis.⁹

Enthesitis Count

Tenderness on examination is recorded as either present (1) or absent (0) for each of the 6 sites, for an overall score range of 0 – 6.

Presence of Enthesitis

If enthesitis is present with any of the 6 sites (lateral epicondyle humerus left and right, Achilles tendon insertion left and right and medial condyle femur left and right), the subject is counted as a subject with enthesitis.

APPENDIX J. SPONDYLOARTHRITIS RESEARCH CONSORTIUM OF CANADA (SPARCC) ENTHESITIS INDEX

Enthesial sites examined include medial epicondyle (left and right), lateral epicondyle (left and right), supraspinatus insertion into greater tuberosity of humerus (left and right), greater trochanter (left and right), quadriceps insertion into superior border of patella (left and right), patellar ligament insertion into inferior pole of patella or tibial tubercle (left and right), Achilles tendon insertion into calcaneum (left and right), plantar fascia insertion into calcaneum (left and right).¹⁰

Enthesitis Count

Tenderness on examination is recorded as either present (1) or absent (0) for each of the 16 sites, for an overall score range of 0 – 16.

APPENDIX K. PSORIATIC ARTHRITIS RESPONSE CRITERIA (PSARC)

A subject is defined as a PsARC responder if, and only if, they have an improvement in two of the following four factors (with at least one factor being a joint count) and no worsening in the remaining factors:¹¹

- Patient global assessment of disease activity (0 – 100 mm VAS scale, improvement defined as decrease of ≥ 20 mm)
- Physician global assessment of disease activity (0 – 100 mm VAS scale, improvement defined as decrease ≥ 20 mm)
- Tender 68-joint count (improvement defined as decrease of $\geq 30\%$)
- Swollen 66-joint count (improvement defined as decrease of $\geq 30\%$)

APPENDIX L. MINIMAL DISEASE ACTIVITY

The proportion of subjects achieving minimal disease activity (MDA) will be analysed.¹² A patient is classified as achieving MDA when at least 5 of the 7 following criteria are met.

- Tender joint count ≤ 1
- Swollen joint count ≤ 1
- PASI ≤ 1 or BSA $\leq 3\%$
- Patient Assessment of Pain-VAS ≤ 15
- Patient Global Assessment of Disease Activity VAS ≤ 20
- HAQ-DI ≤ 0.5
- Tender enthesal points ≤ 1

APPENDIX M. PSA DISEASE ACTIVITY SCORE (PASDAS)

The PASDAS is a weighted index incorporating patient and physician global VAS scores, TJC and SJC, dactylitis and enthesitis, health-related quality of life, and CRP levels.¹³ The following formula is used:

$$(((0.18 \times \text{VPGA}) + (0.159 \times \text{VPtGA}) - (0.253 \times \text{VSF36/PCS}) + (0.101 \times \text{LN}(\text{SJC} + 1)) + (0.048 \times \text{LN}(\text{TJC} + 1)) + (0.23 \times \text{LN}(\text{LEI} + 1)) + (0.377 \times \text{LN}(\text{TDC} + 1)) + (0.102 \times \text{LN}(\text{CRPmg/dl} + 2))) \times 1.5$$

LN = natural logarithm; TDC = tender dactylitis count

APPENDIX N. DISEASE ACTIVITY IN PSORIATIC ARTHRITIS (DAPSA)

DAPSA is an assessment of disease activity in PsA based on the following variables: TJC68, SJC66, PtGA of Disease Activity (VAS), Patient's Assessment of Pain (VAS), and CRP.¹⁴ Minor, moderate, and major response in DAPSA are defined as 50%, 75%, and 85% improvement from baseline (Day 1) respectively.

Calculation: SJC + TJC + PtGA + PP + CRP [mg/dl]

APPENDIX O. ANKYLOSING SPONDYLITIS DISEASE ACTIVITY (ASDAS)

ASDAS will be calculated taking the following variables into account:

- Back pain (question 2 from BASDAI)
- Duration of morning stiffness (question 6 from BASDAI)
- Patient's global assessment of the disease on VAS (0 - 10 cm)
- Peripheral joint pain/swelling (question 3 from the BASDAI)
- Serum CRP level (mg/L)

ASDAS calculation¹⁵

The ASDAS formulas are as follows:

ASDAS-CRP (the preferred version):

$$0.12 \times \text{Back Pain} + 0.06 \times \text{Duration of Morning Stiffness} + 0.11 \times \text{Patient Global} + 0.07 \times \text{Peripheral Pain/Swelling} + 0.58 \times \text{Ln}(\text{CRP} + 1)$$

CRP is in mg/litre; the range of other variables is from 0 to 10; Ln represents the natural logarithm; $\sqrt{}$ represents the square root.

APPENDIX P. HEALTH RESOURCE UTILIZATION QUESTIONNAIRE (HRU)

Since the last study visit has the subject had any visits for their psoriatic arthritis other than the protocol required visit?

YES: ____

NO: ____

If YES, please provide the following:

1. Since the last protocol required visit, has the subject been seen by a health care professional for their psoriatic arthritis?

YES: ____

NO: ____

If YES, how many times: ____

2. Since the last protocol required visit, has the subject been seen in the Emergency Room for their psoriatic arthritis?

YES: ____

NO: ____

If YES, how many times: ____

3. Since the last protocol required visit, has the subject been admitted to the hospital due to their psoriatic arthritis?

YES: ____

NO: ____

If YES, please list the ADMISSION DATE: ____/____/____
DD MMM YYYY

DISCHARGE DATE: ____/____/____
DD MMM YYYY

APPENDIX Q. PATIENT-REPORTED OUTCOMES

BASDAI (Bath Ankylosing Spondylitis Disease Activity Index)¹⁶

Each question is answered on a 0 to 10 scale. For Questions 1 – 5, 0 means none and 10 means very severe; for Question 6, 0 means 0 hours and 10 means 2 or more hours. All questions refer to last week.

1. How would you describe the overall level of fatigue/tiredness you have experienced?
2. How would you describe the overall level of AS neck, back or hip pain you have had?
3. How would you describe the overall level of pain/swelling in joints other than neck, back or hips you have had?
4. How would you describe the overall level of discomfort you have had from any areas tender to touch or pressure?
5. How would you describe the overall level of morning stiffness you have had from the time you wake up?
6. How long does your morning stiffness last from the time you wake up?

Calculation of BASDAI: compute the mean of Questions 5 and 6. Calculate the sum of the values of Questions 1 – 4 and add the result to the mean of Questions 5 and 6. Divide the result by 5.

Patient's Global Assessment of Disease Activity¹⁷

The patient global assessment VAS will be self-administered by the patient.

The patient's global assessment of disease activity will be performed using a horizontal 100 mm VAS, ranging from 0 (very well) to 100 (very poor) after the question:

"Considering all the ways psoriatic arthritis affects you, please indicate with a vertical mark (|) through the horizontal line how well you are doing today."

Health Assessment Questionnaire Disability Index (HAQ-DI)¹⁸

HAQ-DI is a self-reported patient outcome measurement tool commonly used in RA clinical trials to measure physical functioning in RA patients. The HAQ-DI composite score is calculated as the mean of the scores from the 8 following categories with a range of 0 – 3 (0 = no disability; 3 = worst disability): Dressing and Grooming, Rising, Eating, Walking, Hygiene, Reach, Grip, and Activities. The higher the score, the more likely to associate with morbidity and mortality for the RA patient. Under each category there are 2 - 3 items on the amount of difficulty they have in performing specific activities with four response options from 0 (no difficulty) to 3 (unable to do). In addition to these eight categories, there is an AIDS OR DEVICES/HELP FROM OTHER PERSON section ("companion items") that is used to

record the type of assistance, if any, a subject uses for his/her usual activities in each of the eight categories.

Functional Assessment of Chronic Illness Therapy-Fatigue (FACIT-Fatigue)^{19,20}

Response options/scale: Answers are based on a 5-point Likert scale. Responses of "not at all," "a little," "somewhat," "quite a bit," and "very much" are available for each question, and correspond to scores of 0, 1, 2, 3, and 4, respectively. Recall period for items: 7 days.

1. I feel fatigued.
2. I feel weak all over.
3. I feel listless ("washed out").
4. I feel tired.
5. I have trouble starting things because I am tired.
6. I have trouble finishing things because I am tired.
7. I have energy.
8. I am able to do my usual activities.
9. I need to sleep during the day.
10. I am too tired to eat.
11. I need help doing my usual activities.
12. I am frustrated by being too tired to do the things I want to do.
13. I have to limit my social activity because I am tired.

Short Form-36^{21,22}

The Short Form-36 (SF-36) is a 36-item patient reported measure of overall health. The SF-36 consists of eight domains:

- vitality
- physical functioning
- bodily pain
- general health perceptions
- physical role functioning
- emotional role functioning
- social role functioning

- mental health

A scaled score is calculated for each domain as the weighted sum of the questions in the domain. The score for each domain ranges from 0 to 100. The higher the score the less disability; a score of 100 is equivalent to no disability and a score of 0 is equivalent to maximum disability.

EQ-5D-5L²³

Under each heading, please check the ONE box that best describes your health TODAY:

Mobility

- I have no problems walking
- I have slight problems walking
- I have moderate problems walking
- I have severe problems walking
- I am unable to walk

Self-Care

- I have no problems washing or dressing myself
- I have slight problems washing or dressing myself
- I have moderate problems washing or dressing myself
- I have severe problems washing or dressing myself
- I am unable to wash or dress myself

Usual Activities (e.g., work, study, housework, family, or leisure activities)

- I have no problems with doing my usual activities
- I have slight problems with doing my usual activities
- I have moderate problems with doing my usual activities
- I have severe problems with doing my usual activities
- I am unable to do my usual activities

Pain/Discomfort

- I have no pain or discomfort
- I have slight pain or discomfort
- I have moderate pain or discomfort
- I have severe pain or discomfort
- I have extreme pain or discomfort

Anxiety/Depression

- I am not anxious or depressed
- I am slightly anxious or depressed
- I am moderately anxious or depressed
- I am severely anxious or depressed
- I am extremely anxious or depressed

The patient's assessment of health will be performed using a horizontal 100 mm visual analog scale (VAS), ranging from 0 (worst health patient can imagine) to 100 (best health patient can imagine) after the question:

"Please indicate with a vertical mark (|) through the horizontal line how your health is today."

Patient's Assessment of PsA Pain Intensity²⁴

The patient's assessment of PsA pain intensity will be performed using a horizontal 100 mm visual analog scale (VAS), ranging from 0 (no pain) to 100 (severe pain) after the question:

"Please indicate with a vertical mark (|) through the horizontal line the most pain you had from your psoriatic arthritis today."

Work Productivity and Activity Impairment (WPAI) Questionnaire²⁵

The following questions ask about the effect of your psoriatic arthritis on your ability to work and perform regular activities. Please fill in the blanks or circle a number, as indicated.

1. Are you currently employed (working for pay)? _____ No ___ Yes

If NO, check "NO" and skip to question 6.

The next questions are about the **past seven days**, not including today.

2. During the past seven days, how many hours did you miss from work because of problems associated with your psoriatic arthritis? *Include hours you missed on sick days, times you went in late, left early, etc., because of your psoriatic arthritis. Do not include time you missed to participate in this study.*

_____ HOURS

3. During the past seven days, how many hours did you miss from work because of any other reason, such as vacation, holidays, time off to participate in this study?

_____ HOURS

[figure not shown]
4. During the past seven days, how many hours did you actually work?

_____ HOURS (If "0," skip to question 6.)

5. During the past seven days, how much did your psoriatic arthritis affect your productivity while you were working?

Think about days you were limited in the amount or kind of work you could do, days you accomplished less than you would like, or days you could not do your work as carefully as usual. If psoriatic arthritis affected your work only a little, choose a low number. Choose a high number if psoriatic arthritis affected your work a great deal.

Consider only how much psoriatic arthritis affected productivity while you were working.

CIRCLE A NUMBER

6. During the past seven days, how much did your psoriatic arthritis affect your ability to do your regular daily activities, other than work at a job?

By regular activities, we mean the usual activities you do, such as work around the house, shopping, childcare, exercising, studying, etc. Think about times you were limited in the amount or kind of activities you could do and times you accomplished less than you would like. If psoriatic arthritis affected your activities only a little, choose a low number. Choose a high number if psoriatic arthritis affected your activities a great deal.

Consider only how much psoriatic arthritis affected your ability to do your regular daily activities, other than work at a job.

Psoriatic arthritis had no effect on my daily activities

0 1 2 3 4 5 6 7 8 9 10

Psoriatic arthritis completely prevented me from doing my daily activities

CIRCLE A NUMBER
